3.2 Sample size

According to the statistical requirements, the sample size was estimated. The main effect index was the curative effect of angina pectoris symptoms treated for 12 weeks. According to the literature, the total effective rate of basic treatment plus placebo was 67.5%, and the

total effective rate of basic treatment plus experimental drugs was predicted to be 84.3%. Set $\alpha=0.05$, $1-\beta=0.2$, According to the experimental group: control group = 1:1 set up group,

$$n = \frac{P_1 \times (100 - P_1) + P_2 \times (100 - P_2)}{(P_2 - P_1)^2} \times f(a, b)$$

The minimum sample size to meet the statistical requirements was 98.4 cases in each group, and the dropping rate was not more than 20%, 120 cases in each group, a total of 240 cases.

4. Subject selection and withdrawal

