Modern pharmacology shows that flavonoids and terpene lactones are effective components of *Ginkgo biloba* leaves. Experiments show that flavonoids and terpene lactones are beneficial to blood vessel and brain metabolism and inhibit platelet activating factor. Ginkgolides and ginkgolides can significantly improve the oxygen tolerance of brain cells and enhance local brain flow. Ginkgolides have a strong neuroprotective effect. *Salvia miltiorrhiza* can inhibit platelet aggregation, dilate coronary artery, increase the opening of collateral circulation, improve myocardial hypoxia, and also have good scavenging effect of oxygen free radicals. The experiment of *Zingiber officinale* L. showed that *Zingiber officinale* L. oil could reduce the area of myocardial infarction and the level of serum lactate dehydrogenase after myocardial infarction. It has protective effect on myocardial ischemia. It can also slow down the systolic and diastolic blood pressure, slow down the heart rate and reduce the cardiac output. *Allium sibiricum* can inhibit platelet aggregation and reduce serum lipid peroxide and blood lipid. *Euonymus microphylla* can dilate coronary artery, improve myocardial ischemia and reduce oxygen consumption.

Previous clinical trials

1. To observe the clinical effect of Xinnaoning Capsule on angina pectoris of coronary heart disease of qi stagnation and blood stasis type.

From February 2011 to October 2011, Xinnaoning was observed in 309 Hospital

of PLA. Methods: 182 patients with angina pectoris of qi stagnation and blood stasis type were randomly divided into treatment group (102 cases) and control group (80 cases). The control group was treated with routine treatment group (isosorbide mononitrate tablets, aspirin enteric-coated tablets, 100 mg each time, once a day). The treatment group was treated with routine treatment in the control group. Xinnaoning capsule was taken three times a day for 8 weeks. The results are as follows:

Table1 Comparison of improvement effect of angina pectoris between two groups n (%)

Group	n	Markedly effective	effective	invalid	total effective rate
Test	102	34 (33.3)	52 (51)	16 (15.7)	86 (84.3)
Control	80	26 (32.5)	28 (35)	24 (32.5)	56 (67.5)

There were significant differences between groups. , $P < 0.05$

Table2 Comparison of the curative effect of TCM syndromes improvement between two groups before and after treatment

Symptom	Group	n	ME	effective	invalid	TER (%)
Chest pain	T	102	36	56	12	92 (92.2)

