10.2.3 Statistical analysis content

(1) CDAS3.0 statistical software will be used for statistical analysis.

(2) The main therapeutic data set was FAS analysis population, and the therapeutic PPS population was also analyzed.

(3) Except for the superiority test of the main therapeutic indicators, all other statistical tests are carried out by bilateral test, and the difference of P value less than or equal to 0.05 will be considered statistically significant.

(4) The measurements of each visit in different treatment groups will be described by means of standard deviation. Compared with the baseline values at the time of admission, paired t-test was used to compare the differences between before and after admission. Variance analysis was used to compare the changes before and after treatment in each group.

(5) Frequency (constituent ratio) was used to describe the counting data of each visit in different treatment groups. 2 test or non-parametric test were used to test the changes before and after treatment in each group.

(6) Comparability analysis: Comparing demographic data and other basic value indicators to measure the comparability between the two groups.

(7) Compliance analysis: Compare the two groups of patients whether to use the research drugs on time and in quantity, not using the drugs prohibited in the program.

(8) Abscission analysis: χ^2 test will be used to compare the total abscission rate and the abscission rate due to adverse events in each group.

(9) Equilibrium analysis of basic values: using variance analysis or 2 test to compare demographic data and other basic value indicators to measure the two groups of equilibrium.

(10) Effectiveness analysis: PPS and FAS were used to analyze the main indicators and global indicators, and CMH test considering the central effect was used to analyze the efficacy of the two groups. The main effect indicators were selected to treat 12 weeks of angina symptoms, and the placebo was used as the control for statistical test.

(11) Analysis of factors affecting efficacy: If there are significant correlative factors affecting efficacy, these factors should be considered as covariance analysis or logistic regression analysis when comparing the efficacy of the two groups. Detailed list of combined medication is required.

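### The 67.5% control rate behind the sample size is described as a placebo rate, but the matching source describes no placebo and its control row is internally inconsistent

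*Protocol*

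**What the plan says.** Protocol section 3.2, repeated in the abstract's sample size row, takes its two planning rates from unnamed literature. For control, "the total effective rate of basic treatment plus placebo was 67.5" per cent; for test, the "total effective rate of basic treatment plus experimental drugs was predicted to be 84.3" per cent, both for angina symptom efficacy at 12 weeks. It sets α = 0.05, prints 1−β = 0.2 and uses 1:1 allocation. It concludes: "The minimum sample size to meet the statistical requirements was 98.4 cases in each group". After allowing for dropout it plans 120 per arm, 240 in total.

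The pair 67.5% and 84.3% appears in one other place, Table 1 of section 1 (first prior study, 182 patients, 8 weeks). Of that study the protocol says: "The control group was treated with routine treatment group", followed by isosorbide mononitrate and aspirin. The test arm had the same routine treatment plus Xinnaoning. Neither placebo nor blinding is mentioned. The control row of Table 1 (n=80) reads: markedly effective 26 (32.5), effective 28 (35), invalid 24 (32.5), total effective 56 (67.5).

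The second prior study (Table 4, angina after stenting, 8 weeks) reports a control rate of 49/80 = 61.25%, on background drugs and again with no placebo described.

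**The concern.** The control rate is one of the two numbers that fix the sample size, and it has two defects.

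First, it is presented as an observed rate under placebo, while nothing in the protocol reports a placebo-arm rate. The present trial has a blinded placebo, a 2-week placebo run-in, prescribed exercise and 12 weeks of treatment. A rate from an 8-week arm without placebo can serve as an assumption for that setting, but it is not evidence about it. Section 3.1 itself argues that placebo control lowers the improvement that subjects and researchers expect. That is a reason not to carry over, without comment, a difference obtained without placebo.

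Second, the counts and percentages in the source row disagree, so a reader cannot tell whether the study observed 67.5% or 70%. With a planned difference of 16.8 percentage points, 2.5 points matter. If the trial ends without a significant difference, its interpretation will lean on the planned power, and the protocol gives no view of how that power moves with the control rate.

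**Working it through.** **Source row (Table 1, control, n=80).**
- Responder grades: 26 + 28 = 54, and 54/80 = 67.5%.
- Printed percentages: 32.5 + 35 = 67.5, and 67.5 + 32.5 = 100. They agree with one another and with 54.
- Printed counts: 56 + 24 = 80, but 56/80 = 70% and 24/80 = 30%, not 67.5% and 32.5%.
- Three grades: 26 + 28 + 24 = 78, not 80.
- The test row is sound: 34 + 52 + 16 = 102, and 86/102 = 84.3%.

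The row becomes consistent if 24 and 56 are misprints for 26 and 54. It could instead be that 56 is right and a responder grade and the percentages are wrong. The first needs fewer corrections, but the protocol does not contain the means to decide.

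**Reproducing the plan's figure.** Formula in 3.2, rates in per cent: n = [P1(100−P1) + P2(100−P2)]/(P2−P1)² × f.
- P1 = 67.5, P2 = 84.3: (2193.75 + 1323.51)/16.8² = 3517.26/282.24 = 12.462.
- With f = 7.9 (the rounded value for two-sided 0.05 and 80% power): 12.462 × 7.9 = 98.45, which matches 98.4. The unrounded f = 7.849 gives 97.8.
- Taking 1−β = 0.2 literally, as 20% power, gives 15.6. A one-sided 0.05 test at 80% power gives 77.0, and 90% power two-sided gives 130.9. So 98.4 rests on β = 0.2, two-sided.

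**Other control rates in the document, test rate held at 84.3%.**
- 70%: (2100 + 1323.51)/14.3² × 7.9 = 3423.51/204.49 × 7.9 = 132.3.
- 61.25%: (2373.44 + 1323.51)/23.05² × 7.9 = 3696.95/531.30 × 7.9 = 55.0.

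**Power.** Unpooled normal approximation, two-sided 0.05: Φ(|P2−P1|/√{[P1(100−P1)+P2(100−P2)]/n} − 1.96). For 67.5% and n = 120: 16.8/√(3517.26/120) = 3.103; 3.103 − 1.96 = 1.143; Φ = 0.874. The others follow in the same way. The last column uses 120 × 0.8 = 96.

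| Control rate | Origin | n per arm needed | Power at 120 | Power at 96 |
|---|---|---|---|---|
| 61.25% | second prior study, 49/80 | 55.0 | 99% | 96% |
| 67.5% | Table 1, 54/80 and all percentages | 98.4 | 87% | 79% |
| 70% | Table 1, printed count 56/80 | 132.3 | 76% | 67% |

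The 120 column is the more relevant one. Section 10.2.3 makes the full analysis set the main efficacy set, and section 10.2.1 carries earlier measurements forward for missing cases.

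**Sampling uncertainty.** The 95% Wilson interval for 54/80 runs from 57% to 77%. All three rates lie inside it.

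**The case against.** The strongest answer is that 3.2 copies its source faithfully. Table 1 prints 67.5%, the two responder counts give exactly that, and all four percentages agree. The stated 98.4 follows from it. This stands. A reader might infer from the printed 56 that the true control rate was 70% and that the trial is underpowered, but the documents do not support that step.

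Nor is 67.5% plainly optimistic. The second prior study's control rate is lower. Pooling both control arms, even with 56 for the first, gives 105/160 = 65.6%, which needs 81 per arm and has 93% power at 120. That study enrolled patients after stenting, but this trial admits patients with a PCI history, so it is relevant. It is also a rate without a described placebo, so it widens the range and does not confirm 67.5%.

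A reader might also infer that blinded placebo must raise the control response and so cut the power. That is plausible, but the protocol gives no size for it. Exercise and the longer course apply to both arms: if both rates rose by 2.5 points (70% against 86.8%), 91 per arm would be enough. Control rates above 70% with the test arm fixed are assumptions.

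None of this answers the misdescription. The protocol does not report a placebo-arm rate, and 3.2 says that the literature does.

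**Conclusion.** The point holds as one about description and uncertainty. The planning control rate is called a placebo rate although the matching study describes routine treatment for 8 weeks and no placebo, and the row it comes from is internally inconsistent. Neither the rate nor the power is shown to be wrong. Over the control rates found in the document, power at 120 per arm runs from about 99% (61.25%) through 87% (67.5%) to 76% (70%).

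These figures assume a test rate of 84.3%, a two-sided 5% test, 120 analysed per arm and the unpooled formula. That Table 1 is the source is inferred from the match of both rates, since 3.2 cites none. The point is moderate: it changes no analysis and no decision rule, but it concerns an input that fixes the sample size.

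**What to change.** 1. Check the Table 1 control row against the source report and correct whichever entries are wrong.
2. In 3.2 and the abstract, name the source and describe 67.5% as an assumption taken from routine treatment over 8 weeks with no placebo described.
3. State power at 120 per arm for control rates of 61.25%, 67.5% and 70%. If a higher placebo response is also shown, label it as an assumption and say what is assumed for the test arm.
4. In both places, correct 1−β = 0.2 to β = 0.2 (80% power), the reading that reproduces 98.4.

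The cost is one table row and one paragraph, which appears twice. Enrolment stays at 240. The drawback for the sponsor is that the stated power may look less favourable at the upper end of the range.

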Exclusion Criteria	
 1. Severe cardiopulmonary insufficiency (grade III, IV, severe abnormal pulmonary function); 2. Poor control of hypertension (systolic blood pressure (> 160 mmHg) or diastolic blood pressure (> 100 mmHg) after treatment; 3. Complicated with liver and kidney function damage, ALT, AST (> 1.5 times of the upper limit of normal value), or Cr (> the upper limit of normal value), combined with hematopoietic system and other serious primary diseases; 4. Acute myocardial infarction within 3 months after interventional therapy; 5. Cardiac pacemaker; 6. Pregnancy, lactation or pregnancy planning; 7. Anaphylactic constitution or allergic to known ingredients of research drugs; 8. Chest pain caused by other causes (moderate anemia, hyperthyroidism, etc.) 9. Those who participated in other clinical drug trials within one month; 10. According to the judgement of the researchers, it is not advisable to participate in clinical researchers. 11. Other factors affecting ST-T changes in ECG, such as myocardial hypertrophy, left bundle branch block, etc.
Sample size	
According to the statistical requirements, the sample size was estimated. The main effect index was the curative effect of angina pectoris symptoms treated for 12 weeks. According to the literature, the total effective rate of basic treatment plus placebo was 67.5%, and the total effective rate of basic treatment plus experimental drugs was predicted to be 84.3%. set $\alpha=0.05$, $1-\beta=0.2$, according to the experimental group: control group = 1:1 set up group,
 $n = \frac{P_1 \times (100 - P_1) + P_2 \times (100 - P_2)}{(P_2 - P_1)^2} \times f(a, b)$ 
The minimum sample size to meet the statistical requirements was

	98.4 cases in each group, and the dropping rate was not more than 20%, 120 cases in each group, a total of 240 cases.
Effectiveness evaluating indicator	1. Main outcome measures: The curative effect of angina pectoris; 2. Secondary indicators: curative effect of TCM syndromes, grading changes of severity of angina pectoris, changes of attack times per week, nitroglycerin dosage, score of Seattle Angina Scale and incidence of cardiovascular events, blood HCY (blood homocysteine).

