4.8 Exfoliation excluded cases

4.8.1 The withdrawal of the researcher's decision

Subject withdrawal from the study refers to the decision to withdraw the case from the study according to the judgement of the researcher when the selected subjects are unsuitable for further study in the course of the study.

① In the study, patients with aggravated or aggravated conditions, such as increased number of angina attacks, prolonged duration of each attack or aggravated pain, must take emergency treatment measures such as adjusting treatment drugs, hospitalization or surgery;

② In the study, some complications, complications or special physiological changes occurred in the subjects, and it was not appropriate to continue the study;

③ Prohibited drugs prescribed by the scheme were used in the study。

④ In the study, if angina symptoms worsened in the subjects, those who were judged by the researchers to need to take other angina medicines or increase the dosage of drugs were withdrawn as invalid cases。

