10.2 Statistical analysis method

10.2.1 Statistical description

(1) whether it conforms to normal distribution: modifying statistical methods or transforming data when it does not conform;

(2) Whether there is outlier value or not: make statistical and professional analysis to decide whether to choose or not;

(3) Processing the missing value of the main therapeutic index data: When the main therapeutic effect data of individual subjects are missing, the way to fill the missing data is determined from the statistical and professional point of view. For missing cases, the data were transferred from the previous measurements; for missing data, the measurements were made only once, and the mean of all the data was used to fill in the missing data.

(4) The proportion of exfoliated cases: generally not more than 20%, otherwise it should be analyzed and explained;

(5) Descriptive statistical analysis: calculating mean, standard deviation, confidence interval, maximum, minimum, median, frequency (constituent ratio), etc.

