10.2.2 Statistical expression

(1) The report is mainly expressed in tables, which are self-evident, i.e. with headings, annotations and examples.

(2) The results of repeated measurements can be expressed in tables or statistical charts to increase readability.

(3) Bilateral tests are used in statistical tests. Those whose P is less than or equal to 0.05 will be considered as having statistical significance.

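### The sample-size statement prints power as 20% although 98.4 per arm corresponds to 80%, and 120 per arm covers about 18% dropout rather than the stated 20%

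*Protocol*

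**What the plan says.** Section 3.2 takes the 12-week angina symptom response as the primary outcome, with total effective rates of 67.5% on placebo and 84.3% on test drug, both added to basic treatment, and 1:1 allocation. It fixes the error rates as "Set $\alpha=0.05$, $1-\beta=0.2", prints a formula for two proportions with a multiplier f(a, b) whose value is not given, and concludes: "98.4 cases in each group, and the dropping rate was not more than 20%, 120 cases in each group", 240 in total. The Sample size row of the abstract repeats the same power setting and the same numbers. Neither place mentions 80% power or says whether α is one- or two-sided.

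Three other places bear on the point:

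- **Dropout and missing data.** Section 10.2.1 item (4) uses the same 20% limit: "The proportion of exfoliated cases: generally not more than 20%, otherwise it should be analyzed and explained". Item (3) says "For missing cases, the data were transferred from the previous measurements". Section 4.8.1 item 4 says that subjects whose worsening angina needs other or more medication "were withdrawn as invalid cases".
- **General rule on sidedness.** Section 10.2.2 item (3): "Bilateral tests are used in statistical tests", with significance at P ≤ 0.05.
- **Exception.** Section 10.2.3 item (3): "Except for the superiority test of the main therapeutic indicators, all other statistical tests are carried out by bilateral test".

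**The concern.** Power is 1−β, so a printed 1−β of 0.2 means a one-in-five chance of detecting the assumed effect. No trial would be designed that way, and the sample size beside it is far too large for it, so one of the two figures must be wrong. Separately, a dropout allowance should still hold at its own limit. If 20% are lost from 120, fewer remain than the minimum the protocol has just calculated.

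As printed, a reader can take neither the design power nor the dropout cover from the text. The sidedness conflict concerns type I error rather than power. If the exception for the primary test were taken to mean one-sided 0.05, the error rate in the favourable direction would be 0.05 instead of the 0.025 that underlies the sample size.

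**Working it through.** **Inputs.** All are from section 3.2: P1 = 67.5, P2 = 84.3, α = 0.05, 1:1 allocation, minimum 98.4 per arm, dropout up to 20%, final 120 per arm. The formula is n = [P1(100 − P1) + P2(100 − P2)] / (P2 − P1)² × f, where f = (z for α + z for power)².

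**Step 1: reproduce the 98.4.**

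- Numerator: 67.5 × 32.5 + 84.3 × 15.7 = 2193.75 + 1323.51 = 3517.26.
- Denominator: 16.8² = 282.24.
- Ratio: 3517.26 / 282.24 = 12.462.
- Implied multiplier: 98.4 / 12.462 = 7.896.

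| α and power | f | n per arm |
|---|---|---|
| two-sided 0.05, 80% (same as one-sided 0.025, 80%) | 7.849 | 97.8 |
| the same, f rounded to 7.9 | 7.9 | 98.4 |
| two-sided 0.05, 20% (as printed) | 1.251 | 15.6 |
| one-sided 0.05, 80% | 6.183 | 77.0 |
| one-sided 0.05, 90% | 8.564 | 106.7 |
| two-sided 0.05, 90% | 10.507 | 130.9 |

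Of these settings, only 80% power at two-sided 0.05 (or one-sided 0.025) reproduces the protocol's figure. The 0.2 is therefore β.

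**Step 2: the dropout allowance.**

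- Remaining at the 20% limit: 120 × 0.8 = 96, which is below 98.4.
- Needed for 20%: 98.4 / 0.8 = 123 per arm, so the shortfall is 3 per arm. With the exact f it is 97.8 / 0.8 = 122.3.
- Dropout that 120 covers: 1 − 98.4/120 = 18.0%, or 1 − 97.8/120 = 18.5% with the exact f.
- Multiplying instead of dividing gives 98.4 × 1.2 = 118.1. Rounding that up may be how 120 arose, but the protocol does not say.

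**Step 3: what the gap costs.** Power at 67.5% against 84.3%, two-sided 0.05, normal approximation:

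| n per arm | unpooled variance | pooled variance |
|---|---|---|
| 98.4 | 80.2% | 79.1% |
| 96 | 79.3% | 78.1% |

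The loss is about 1 percentage point.

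**Step 4: sidedness.** The sample size matches two-sided 0.05, as section 10.2.2 requires. Section 10.2.3 item (3) takes the primary superiority test out of that rule and gives neither a direction nor a level. A one-sided 0.05 reading would need only 77.0 per arm, so it is not what the 98.4 was built on. With 96 evaluable per arm it would have 87.1% power (unpooled), against 79.3% two-sided.

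**Step 5: the full analysis set.** Its power cannot be taken from step 3, because it depends on how dropouts are scored. As an outer bound only, suppose every dropout in both arms counts as a failure, so that each rate is multiplied by (1 − d) and all 120 per arm are analysed. At d = 20% the rates become 54.0% and 67.4%. Power (unpooled) is then 80% at 5% dropout, 72% at 10% and 58% at 20%. The protocol does not prescribe this rule.

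**The case against.** The power error is harmless in practice: the formula and rates show plainly that 0.2 is β, the text is a translation, and nothing in the design changes. That is right about the consequence, but the figure is wrong in both places where it appears, and the reader has to solve for f to find the design power.

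The dropout gap is close to rounding. The loss of 0.9 points of power is smaller than the 1.1-point difference between the pooled and unpooled calculations at the same n. The 20% can also be read as an upper limit rather than a planning value, and section 10.2.1 item (4) is a trigger for explanation, not a second planning assumption. All of this stands as to size. An allowance with an upper limit should nevertheless hold at that limit, and here it does not.

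Nor is 96 evaluable per arm the primary analysis. Section 10.2.3 item (2) makes the full analysis set primary, and sections 4.8.2 and 10.2.1 keep many withdrawals in it by carrying values forward. This also stands: the shortfall concerns mainly the per-protocol set and subjects with no usable data. It is the reason for giving no full-analysis-set power beyond a labelled bound.

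Finally, the protocol never says one-sided 0.05, and an analysis plan could set the level. That is why the type I error consequence is put conditionally. The conflict between sections 10.2.2 and 10.2.3 is still within the protocol itself and should be removed there.

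**Conclusion.** The concern holds and is minor. The printed power of 20% is wrong; the sample size was calculated for 80%. The 120 per arm covers 18.0% dropout (18.5% with the exact multiplier), 3 per arm short of what 20% requires, at a cost of about 1 point of power. This rests on the protocol's own rates and formula, and on treating dropouts as lost to the analysis. It does not show that the trial is underpowered.

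The sidedness of the primary test is unresolved in the text. The sample size supports two-sided 0.05 or, equivalently, one-sided 0.025. A one-sided 0.05 test would double the favourable-direction error from 0.025 to 0.05.

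**What to change.** - In section 3.2 and the abstract, replace the power setting with β = 0.2 (power 80%), two-sided α = 0.05, f = 7.9.
- In the same places, state that 120 per arm covers about 18% dropout, or that at 20% dropout the 96 evaluable per arm give about 79% power (78% with pooled variance).
- Reword section 10.2.3 item (3) to agree with section 10.2.2, so that the primary test is two-sided at 0.05 (or one-sided at 0.025). Do this before the first unblinding.
- Do not print a power figure for the full analysis set.

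The cost is a rewording of section 3.2, the abstract and one sentence in section 10.2.3. The sample size, endpoint and conduct stay as they are. Fixing the level forgoes the extra power that a one-sided 0.05 test would have had: about 79% instead of 87% with 96 evaluable per arm.
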